4. POTENTIAL BENEFITS OF THE PROPOSED RESEARCH TO THE SUBJECTS AND OTHERS

There is emerging evidence that a single administration of psilocybin produces antidepressant effects in individuals with treatment-resistant depression (i.e., individuals not responding to > 2 trials of antidepressants; Carhart-Harris et al., 2016). Psilocybin increases trait-levels of openness, and it engenders feelings of connectedness and a greater sense of meaning and purpose (Griffiths et al., 2011; MacLean et al., 2011). In the general population, these perceptual and cognitive changes are strongly felt and endure for months following one administration (Griffiths et al., 2006). Psilocybin may be a catalyst for the cognitive and behavioral changes that are sought in psychotherapy. In combination with CBT, it is possible that these effects are magnified.

The risks of psilocybin are minimal, especially with the strict eligibility criteria and screening that will take place for this study. There are no significant risks of CBT. Both treatments are known to have antidepressant effects for individuals with major depressive disorder. Their combination has the potential of magnifying their individual antidepressant effects in the short-term by creating greater reductions in depressive symptoms and in the long-term by leading to more sustained recovery of symptoms. Additionally, the potential benefit for society at-large is significant. Developing an evidence-based psychosocial treatment protocol to adjoin psilocybin treatment can help to improve the safety and efficacy of the drug treatment if/when psilocybin is delivered as a therapeutic agent to the public.

5. IMPORTANCE OF THE KNOWLEDGE TO BE GAINED

There are currently no manualized treatment protocols to guide clinicians in the psychosocial treatment that adjoins psilocybin. Developing an evidence-based psychosocial treatment protocol to adjoin psilocybin treatment can help to improve the safety and efficacy of the drug treatment if/when psilocybin is delivered as a therapeutic agent to the public. Additionally, the potential efficacy of psilocybin-assisted CBT for depression could provide benefit to many affected individuals and their family members who are averse to or otherwise unhelped by current medication approaches.

Appendices.

Appendix I. Case Report Form

Appendix II. Music Playlist

Appendix III. Drug Management Protocol

Appendix IV. Security Provisions for Drug Storage

Appendix V. Controlled Substances Usage Log

Appendix I. Case Report Form

DCI
Cancel

Subject ID: _____ Date: _____ Monitors: _____ Session: 1-10mg

Ideal Time	Actual Time	Activity	BP	HR	Rescue drug administered	Study Questionnaires	Persisting effects	Oriented X4	Important Event Reporting
8:00		U-tox & pregnancy screen							
8:30		Review study procedures							
9:00		Administer Psilocybin							
9:30		Time Point 1							
10:00		Time Point 2							
10:30		Time Point 3							
11:00		Time Point 4							
11:30		Time Point 5							
12:00		Time Point 6							
12:30		Time Point 7							
1:00		Time Point 8							
1:30		Time Point 9							
2:00		Study Questionnaires							
3:00		Discharge							

*Bolded activities require BP and HR measurement

BASELINE QUESTIONS	
Last food: _____	Unusual physical symptom or stress: Y / N
Last caffeine: _____ or Not Regular User	(Must be N)
Normal? Y / N	Anti-hypertensive medication taken: Y / N / NA
Last nicotine: _____ or Not Regular User	(Must be taken as prescribed within past 24 hours, if prescribed)
Normal? Y / N	Pregnancy Test: Positive / Negative
Last alcohol: _____ or Not Regular User	(Must be negative)
(Must be > 1 day)	Drug Test: Positive / Negative
Last cannabis: _____ or Not Regular User	(Must be negative)
(Must be > 30 days)	Identified support person for pick up:
Last PRN: _____ or Not in Last Month	
(Must be > 6 hours)	

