- Resting blood pressure above 140 systolic, 90 diastolic or heart rate > 90 beats per minute (averaged across four separate measurements)
- Meeting criteria for a DSM-5 cluster B personality disorder (narcissistic, histrionic, borderline, antisocial personality disorder),
- Active suicidality (i.e., HAM-D item 3 score of 3 or greater) or other psychiatric disturbance requiring acute treatment

- Current use of antidepressants or other serotonergic-affecting substances (e.g., St. John's Wort and 5-hydroxytryptophan), lithium, or efavirenz [regardless of whether the drug(s) is/are prescribed for MDD or other conditions]
- Current use of opioids (e.g., codeine, fentanyl, hydrocodone, meperidine, tramadol)
- Currently receiving cognitive behavioral therapy,
- Any of the following cardiovascular conditions: uncontrolled hypertension, coronary artery disease, congenital long QT syndrome, cardiac hypertrophy, cardiac ischemia, congestive heart failure, myocardial infarction, tachycardia, artificial heart valve, a clinically significant screening ECG abnormality, or any other significant cardiovascular condition
- QTc interval measurement of > 450 ms in males or > 460 ms in females as measured by the baseline ECG
- A history of stroke or Transient Ischemic Attack (TIA)
- Epilepsy or history of seizures
- Insulin-dependent diabetes
- Meeting criteria for a DSM-5 substance abuse or dependence within prior 6 months (including for nicotine and cannabis)
- Positive urine drug screen for illicit substances (not including cannabis)
- Use of other psychedelics or ketamine within prior 12 months
- Adverse prior reaction to a 5-HT_{2A} receptor agonist psychedelic agent
- Pregnant, trying to get pregnant, or nursing

SCREENING AND TESTING PROCEDURES:

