agents, lithium, or efavirenz (regardless of whether the drug(s) is/are prescribed for a depressive disorder or another condition). Additionally, participants will be excluded if they are taking agents that may interact with psilocybin metabolism/effects (e.g., antipsychotics, other dopamine antagonists) or agents that may increase the risk of psychotic symptoms (e.g., dopamine agonists, stimulants). The study team will not work with subjects to taper them off medications. Subjects will be excluded if they, prior to screening, have not already discontinued any medications excluded for this study.

The results of the physical screening (including the blood panels, urine toxicology, and ECG) will be reviewed by a study physician. To be eligible, participants must have a clear ECG screening (no clinically significant abnormalities and QTc measurement > 450 milliseconds in males or > 460 milliseconds in females). Participants will also be excluded if they report or are found to have any cardiovascular conditions, including uncontrolled hypertension, coronary artery disease, congenital long QT syndrome, cardiac hypertrophy, cardiac ischemia, congestive heart failure, myocardial infarction, tachycardia, artificial heart valve, a clinically significant screening ECG abnormality, or any other significant cardiovascular condition. A personal history of stroke, Transient Ischemic Attack (TIA), hepatic impairment, epilepsy, and insulin-dependent diabetes will also be exclusionary. Individuals who have any medical conditions or take medications that are exclusionary for this study will be withdrawn from the study. In addition to a negative pregnancy test, women of child-bearing potential will need to be on at a form of highly effective contraception (e.g., oral contraceptive pill) for at least one month prior to study entry and for the duration of the study.

For individuals with whom the study physician requires more clarification regarding their medical condition(s) or medications, a release of information (ROI) will be obtained to consult with the participant's primary care physician. For participants with which the study physician cannot gather a clear medical history or in which there is ambiguity around whether they meet criteria for any of the above-mentioned conditions will be excluded from the study. Participants who do not clear the medical screening will be withdrawn from the study.

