Participants must agree not to take other drugs while taking part in this study unless approved by the study team. Participants must not use illicit drugs and you must report to us the use of any prescribed, over-the-counter, or herbal medications. Subjects who test positive for illicit drugs or alcohol at any of the study screenings will be removed from the study. Psilocybin may interact with antidepressant medications and other serotonergic agents. Therefore, participants cannot proceed past the study screening if they are currently on serotonergic agents. If participants need to start taking a restricted drug during the study, they will not be administered psilocybin but will otherwise remain in the study. Restricted drugs which may interact with psilocybin include:

- **Selective serotonin reuptake inhibitors (SSRIs)**, such as fluoxetine (Prozac), sertraline (Zoloft), paroxetine (Paxil), citalopram (Celexa), and escitalopram (Lexapro), and fluvoxamine,
- **Serotonin and norepinephrine reuptake inhibitors (SNRIs)**, such as venlafaxine (Effexor), desvenlafaxine (Pristiq), duloxetine (Cymbalta), and levomilnacipran (Fetzima),
- **Atypical antidepressants**, such as bupropion (Wellbutrin), mirtazapine (Remeron), trazodone (Oleptro), vortioxetine (Brintellix), vilazodone (Viibryd), and milnacipran (Savella),
- **Tricyclic antidepressants**, such as clomipramine, amitriptyline, imipramine (Tofranil), nortriptyline (Pamelor), desipramine (Norpramin), doxepin, trimipramine (Surmontil), and protriptyline (Vivactil),
- **Monoamine oxidase inhibitors (MAOIs)**, such as Selegiline (Emsam), tranylcypromine (Parnate), phenelzine (Nardil) and isocarboxazid (Marplan),
- **Tetracyclic antidepressants**, such as maprotiline,
- **Serotonin modulators**, such as nefazone (Serzone),
- **Agents that may be associated with serotonin syndrome**, such as lithium, efavirenz (Sustiva), St. John's Wort, and 5-hydroxytryptophan, opioids, buspirone, carbamazepine
- **Agents that may interact with psilocybin metabolism/effects**, such as serotonin antagonists (e.g., cyclobenzaprine, ondansetron), antipsychotics, dopamine antagonists, nicotine, modulators of uridine diphosphate (UDP) or glucuronosyltransferase
- **Agents that may increase the risk of psychotic symptoms**, such as carbidopa-levodopa, dopamine agonists, stimulants, anticholinergics, N-methyl-D-aspartate (NMDAR) antagonists

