If participants must take a nonprescription medication, participants will be asked to stop using it for 24 hours before a psilocybin session. Pain relievers containing only aspirin, ibuprofen, or acetaminophen are acceptable for normal use without special permission. Participants must also agree to leave urine samples upon request or to take a breathalyzer test to allow the study team to monitor participants' compliance with the drug and alcohol restrictions.

-Cognitive behavioral therapy (CBT)

There are no significant risks of CBT; however, CBT does involve asking patients to engage in activities that can be aversive and/or opposite of their typical thoughts and behaviors. As such, participants may experience discomfort as a result to engaging in CBT skills such as cognitive restructuring, behavioral activation, relaxation exercises.

-Depressive symptoms

Cognitive-behavioral therapy and psilocybin have been shown to have a beneficial effect of depressive symptoms. Nonetheless, it is possible that depressive symptoms will worsen during the study. An increase in depressive symptoms could be due to the study interventions (including psilocybin), not continuing in standard clinical care, or the natural course of depression. Depressive symptoms which could worsen include, but are not limited to: suicidal thoughts, low mood, feeling hopeless or guilty, fatigue, lack of pleasure, poor concentration, and change in sleep or appetite.

-Alcohol restrictions

The effects of psilocybin may interact with alcohol. This means that if participants consume alcohol while the drug is in their system, they could experience magnified or unpredictable effects of the drug, which could impair their ability to do everyday tasks such as driving an automobile. Such undesirable effects are possible for at least 24 hours following a visit to the research unit. Therefore, participants will be asked to not consume alcohol for a period of at least 24 hours before and 24 hours following the psilocybin session.

-Activity restrictions

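### The session 1 form's single PRN check (more than 6 hours) does not apply the protocol's 24-hour limits for nonprescription and psychoactive medicines

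*Combined protocol and SAP*

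**What the plan says.** Three rules in the body of the protocol bear on medicines taken shortly before a drug session.

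- **Nonprescription medicines** (Potential Risks, Drug and medication restrictions). If one must be taken, "participants will be asked to stop using it for 24 hours before a psilocybin session". The exception is: "Pain relievers containing only aspirin, ibuprofen, or acetaminophen are acceptable for normal use without special permission".
- **Psychoactive drugs** (Study Inclusion and Exclusion Criteria). Participants undertake to avoid any of them, alcohol included, for 24 hours before each session. Usual caffeine is allowed.
- **PRN medicines** (same list, separate criterion). Participants undertake to take none on session mornings.

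The form in Appendix I is the one for session 1 (10 mg). It asks for the time of the last PRN medicine and sets the pass mark at "Must be > 6 hours". It has its own lines for alcohol (more than 1 day), cannabis (more than 30 days) and a negative drug test. It has no other line for nonprescription or psychoactive medicines.

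Many agents are barred regardless of timing. The exclusion criteria list "Current use of opioids (e.g., codeine, fentanyl, hydrocodone, meperidine, tramadol" and serotonergic agents. Screening and Testing Procedures adds that "participants will be excluded if they are taking agents that may interact with psilocybin metabolism/effects", with antipsychotics among the examples. The restricted list also covers "dopamine agonists, stimulants, anticholinergics, N-methyl-D-aspartate (NMDAR) antagonists".

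**The concern.** The form holds the pass marks that staff check before dosing. For alcohol it carries the protocol's 24-hour limit across. For medicines it has one 6-hour line that does not distinguish by type. A PRN medicine that is also nonprescription or psychoactive falls under a 24-hour limit as well as the morning rule, and the form tests only something close to the morning rule. Staff could complete the form correctly and still dose a participant who is outside the protocol's limits.

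What is at stake is participant safety and compliance on the dosing day. The HAM-D, GAF, CSQ-8 and feasibility analyses are untouched.

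**Working it through.** No statistical quantity is involved. The check compares clock times and then asks which products are affected.

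**Inputs.** Form limit: 6 hours (Appendix I). Protocol limits: 24 hours (Drug and medication restrictions; inclusion criteria). Ideal times on the form: 8:00 for the first activity and 9:00 for dosing. Planned participants: 30 (General Investigational Plan).

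**Main case, both limits counted back from dosing**

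- Form cut-off: 9:00 − 6 h = 3:00 on the session day.
- Protocol cut-off: 9:00 − 24 h = 9:00 the previous day.
- Use that passes the form but is inside the 24 hours: 9:00 the previous day to 3:00, which is 24 − 6 = 18 hours.
- Morning rule: the protocol does not say when morning starts. If it starts at midnight (an assumption), the rule already covers 0:00 to 3:00, leaving 18 − 3 = 15 hours.

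**Other reference times.** The documents do not say whether the intervals run to arrival (8:00) or to dosing (9:00).

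| 24 h counted from | 6 h counted from | Window | Length | Before midnight only |
|---|---|---|---|---|
| 9:00 | 9:00 | 9:00 to 3:00 | 18 h | 15 h |
| 9:00 | 8:00 | 9:00 to 2:00 | 17 h | 15 h |
| 8:00 | 8:00 | 8:00 to 2:00 | 18 h | 16 h |
| 8:00 | 9:00 | 8:00 to 3:00 | 19 h | 16 h |

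The gap is 17 to 19 hours, or 15 to 16 after the morning rule. The choice of reference time matters little.

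**Example.** A product taken at 22:00 is 11 hours before a 9:00 dose. That is more than 6, so it passes the form. It does not breach the morning rule. It is less than 24, so it breaches the protocol limit.

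**Which products are affected**

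| Product | Protocol | Conflict with the form |
|---|---|---|
| Agents already barred (opioids, serotonergic agents, antipsychotics, stimulants, anticholinergics, NMDAR antagonists) | Not permitted at any interval | None; the 6-hour line does not decide these |
| The three named pain relievers | Normal use accepted | None |
| Prescribed, non-psychoactive PRN medicines | Morning rule only | None with the 24-hour limits |
| Other nonprescription products, not barred | 24 hours | Yes |
| Psychoactive medicines, not barred | 24 hours, on the plain reading | Yes, on that reading |

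**Count.** The form shown covers at most 30 × 1 = 30 sessions, if all 30 participants are dosed. The session 2 form is not shown. No rate of PRN use is given, so the number affected cannot be estimated.

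**The case against.** The best defence is that the 6-hour line carries out the one protocol rule that names PRN medicines, the ban on session mornings, and roughly matches it. The psychoactive criterion is separate and can be read as covering substances rather than medicines; on that reading the alcohol, cannabis and drug-test lines already implement it. Other controls also exist: "Participants must agree not to take other drugs while taking part in this study unless approved by the study team", and participants must "agree to leave urine samples upon request or to take a breathalyzer test". The form records the actual time of the last PRN, the monitors are psychologists and/or psychiatrists, and a study physician prescribes the dose.

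Much of this stands. It narrows the point and lowers its weight, and it leaves the psychoactive limb as the plain reading but not the only one. It does not answer the nonprescription limb, where the 24-hour limit is expressly about medicines. Nor do the other controls supply a 24-hour check: team approval carries no stated interval before dosing, the compliance tests just quoted are on request, and the routine session-day urine screen is for illicit drugs.

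Three stronger readings are tempting, and the documents do not support them.

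- *A PRN benzodiazepine is plainly permitted because the restricted list does not name it.* The lists are given as examples, not as complete. They cover agents that may alter psilocybin's effects, and Safety Measures uses diazepam against distress during sessions. Its status is unclear. The documents also describe no harm from adding rescue diazepam to an earlier dose.
- *A breach has no consequence.* Participant Monitoring and Removal from the Study has a general rule withdrawing participants who do not comply with study procedures. Its examples are missed therapy sessions and refused follow-up, but it is not limited to them. What is missing is a specific rule for this situation.
- *18 of 24 hours means that 75% of sessions or participants are exposed.* It is a share of the clock only.

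**Conclusion.** The form's threshold is inconsistent with the protocol's own limits and is wrong as written, at low severity. For nonprescription products that are neither barred nor among the three named pain relievers, the inconsistency follows directly from the text. For psychoactive medicines not already barred, it rests on the plain reading of the inclusion criterion.

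The size is 18 hours with both intervals counted from a 9:00 dose, falling to 15 if morning starts at midnight. The finding concerns the session 1 form alone; whether session 2 uses the same line cannot be told. It has no bearing on sample size, endpoints or analysis.

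**What to change.** Keep the existing 6-hour PRN line for other PRN medicines, and add two lines to the form for each session:

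1. Last nonprescription medicine, other than the three permitted pain relievers: must be more than 24 hours ago.
2. Last psychoactive medicine, prescribed or not, excluding usual caffeine: must be more than 24 hours ago, as for alcohol. Nicotine is outside this point.

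State next to these lines whether a failed check postpones the session, since the general noncompliance rule speaks only of withdrawal. If the sponsor means the psychoactive criterion to cover substances and not medicines, the criterion should say so, and line 2 is then not needed.

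The cost is form wording. Both lines apply limits the protocol already sets (line 2 on the plain reading), so they add no restriction, visit or test. The downside is an occasional postponed session; the documents give no rate from which to estimate how often.

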Appendix II. Music Playlist

**PLAYLIST, MAJOR DEPRESSIVE DISORDER
STUDY****Arrival and Ingestion***

MINUTE	SECONDS	
	S	

		Antonio Vivaldi, Andante, Concerto RV 532 in G Major for 2 guitars, strings & continuo, Guitar Concertos, Los Romeros, Academy of St. Martin-in-the-Fields, Philips 412-624-2.
3	32	
		Antonio Vivaldi, Largo, Concerto RV93 in D Major for guitar, strings & continuo, Ibid.
3	55	
		Antonio Vivaldi, Largo, Concerto RV 356 in A Minor for guitar, Ibid.
2	22	
		Paul Horn "Mumtaz Mahal", Inside the Taj Mahal, Kuckuck, LC2099.
3	26	
5	42	
		Paul Horn "Shah Jahan", Inside the Taj Mahal, Ibid.
		Ron Korb, "Flute Traveller (Alto Flute), Oasis Productions Limited, SOCAN NHCD 205.
2	22	
		JS Bach: Suite No. 3 (Bach) Brazilian Guitar Quartet, Delos B00004YR6P
6	46	
		Russill Paul "By the Stream" (PM Yoga Chants), Gaia, The Relaxation Company, CD 3142.
10	57	
		"Om Namah Shivaya" (CD from "Yoga of Sound"), Novato CA: New World Library, 2004.
2	32	
		Edward Elgar, "Nimrod", Enigma Variation #9, Leonard Bernstein, The Artist's Album, DGG 457 691-2.
6	18	
		Morten Lauridsen "O Magnum Mysterium", A Robert Shaw Christmas: Angels on High, Telarc20 CD-80461.
6	17	
		"Alleluia, Behold the Bridegroom", Sacred Treasures III: Choral Masterworks from Russia and Beyond, St. Petersburg Chamber Choir, Hearts of Space, 02504111423.
5	32	

59 minutes, 41 seconds

		Henryk Gorecki, "Lento--Sostenuto Tranquillo ma Cantabile" (Symphony #3, Movement #1), London Sinfonietta, David Zinman, Dawn Upshaw, Elektra Nonesuch 9 79282-2.
26	49	
		Johannes Brahms, "Selig sind, die da Leid tragen" (Ein Deutsches Requiem), San Francisco Symphony & Chorus, Herbert Blomstedt, London 443 771-2.
10	41	
		Johannes Brahms, "Denn alles Fleish es ist wie Gras" (Ein Deutsches Requiem), Ibid.
14	39	

		Johannes Brahms, "Adagio, Non Troppo" (Symphony No. 2, Op. 73), New York Philharmonic, Leonard Bernstein, Sony SMK 61829.
10	16	
		Johannes Brahms, "Wie lieblich sind Deine Wohnungen" (Ein
5	42	Deutsches Requiem), Op. cit.
		J.S. Bach, "Kyrie" (Mass in B Minor), Robert Shaw, Atlanta Symphony
10	26	& Chamber Chorus, Telarc CDE-80233.
4	28	J.S. Bach, Completion of "Kyrie" (Omitting "Christe Eleison" duet)

1 hour, 23 minutes, 01 second

		Samuel Barber, "Adagio for Strings" New York Philharmonic, Leonard
10	2	Bernstein, Sony, SMK 63088
		J.S. Bach, "Largo" (Concerto for 2 Violins in D Minor), Hillary Hahn &
		Margaret Batjer, Bach-Concertos, Los Angeles Chamber Orchestra,
6	50	Deutsche Grammophon, 474 6392
		Antonio Vivaldi, "Et in terra pax" (Gloria in D Major), Atlanta
6	2	Symphony, Robert Shaw, Telarc CD-80194
		J.S. Bach, "Komm suesser Tod" (Bach/Stokowski), Full Dimensional
5	57	Sound, EMI CDM 7243 5 66385 2 5
		W.A. Mozart, "Laudate Dominum", Vesperae solennes de confessore,
		Kiri Te Kanawa, London Symphony, Sir Colin Davis, Philips 412 873-2
5	15	
		Max Bruch, "Kol Nidrei", Op. 47, Jacqueline Du Pre & Daniel
12	4	Barenboim, Brahms Cello Sonatas, EMI

46 minutes, 10 seconds

		Johannes Brahms, "Adagio", Concerto for Violin & Orchestra in D
		Major, Opus 77, Chicago Symphony, Fritz Reiner, Jascha Heifetz, HMG
8	18	09026-61742-2.
		Henryk Gorecki, "Lento e Largo--Tranquillissimo", Symphony No. 3,
9	47	Op. 36,(Movement #2), Op. cit.
		Sir Edward Elgar, "Larghetto" (Serenade for String Orchestra in E
6	33	Minor, Op. 20), Halle, Mark Elder, CD HLL 7501.
		Gabriel Faure, "In Paradisum", Requiem, Op.48, Choir of St. John's
3	49	College, Cambridge, George Guest, London 436-486-2.
		W.A. Mozart, "Adagio", Clarinet Concerto KV622, Jean-Francois
7	14	Paillard, Jacques Lancelot, Erato 2292-45978-2
		Arvo Part, "Cantus in Memory of Benjamin Britten", from "Sanctuary",
		Bournemouth Sinfonietta, Richard Studt, Virgin Classics, CSC 7243 5
6	19	45314 2 2
		Arvo Part, "Nunc Dimittis", Sabat Mater, Black Box, BBM1071
6	55	
27	38	El-hadre 2, the Mystik Dance, Klaus Weise, CD-263 (latter half)

- | | | |
|----|----|--|
| | | Ludwig van Beethoven, "Adagio un poco moto", Piano Concerto #5 ("Emperor"), Leon Fleisher, George Szell, Cleveland Orchestra, Sony |
| 8 | 37 | "Essential Classics", SBK 46549. |
| | | Russill Paul, "Om Namah Shivaya", Shakti Yoga, The Yoga of Sound, |
| 17 | 37 | The Relaxation Company, CD 3133 |
| | | WA Mozart, "Ave Verum Corpus" (KKV618, London Symphony, Colin |
| 4 | 3 | Davis, Phillips: 412 873-2. |
| | | Gustav Mahler, "Adagietto" (Symphony #5), Lorin Maazel, Vienna |
| 10 | 31 | Philharmonic, Sony 696998985025, |

1 hour, 57 minutes, 21 seconds

- | | | |
|----|----|---|
| | | Alan Hovhaness, "Andante con moto", Symphony #2, "Mysterious Mountain," Seattle Symphony, Gerard Schwarz, Telarc 089408060427. |
| 7 | 47 | |
| | | Joseph Canteloube, "Bailero", Songs of the Auvergne, Orchestre de l'opera National de Lyon, Kent Nagano, Dawn Upshaw, Erato 0630- |
| 5 | 42 | 17577-2. |
| | | Richard Strauss, "Moderato", Death and Transfiguration, Andre Previn, |
| 2 | 10 | Wiener Philharmoniker, Telarc. CD-80167 |
| 6 | 2 | Richard Strauss, "Tranquillo", Death and Transfiguration, Ibid. |
| | | Russill Paul, "Evening Shadows Fall", Nada Yoga, The Yoga of Sound, |
| 23 | 31 | Gaiam, The Relaxation Company, CD 3133. |
| | | J.S. Bach, "Passacaglia & Fugue in C Minor", Bach/Stokowski, Full |
| 14 | 51 | Dimensional Sound, EMI: CDM 7243 5 66385 2 5. |
| | | Arvo Part, "Spiegel im Spiegel for violin and piano", Sabat Mater, |
| 8 | 15 | Black Box, BBM1071 |

1 hour, 8 minutes, 18 seconds

- | | | |
|----|----|---|
| 3 | 3 | Enya, "Storms in Africa II", Watermark, Reprise 9 26774-2. |
| | | Guem, "Transe", Musique de Transe, Le Chant Du Monde LDX |
| 5 | 38 | 2741008 |
| 4 | 1 | Adiemus, "Adiemus", Pure Moods, Virgin, 724384218621. |
| | | Gipsy Kings, "Caminando Por la Calle", Mosaique, Nonesuch, |
| 4 | 22 | 075596089227. |
| | | Mercedes Sosa, "Gracias a La Vida", Gracias a la Vida, Polygram |
| 4 | 27 | International, 042283231429. |
| | | Louis Armstrong, "What a Wonderful World", What a Wonderful |
| 2 | 21 | World, Double Play (Intercontinental 600), 607707405826. |
| | | "Ocean Waves", Echos of Nature: The Natural Sounds of the |
| 60 | 9 | Wilderness, Delta, 018111591621. |

1 hour 24 minutes, 01 seconds

Total Duration: 7 hours, 40 minutes, 54 seconds

